6.3 Analysis of AAGA event proportion

Brice questionnaire and Suspected AAGA follow up responses will be analysed to determine the incidence of suspected AAGA in patients undergoing GA for obstetric indication surgery. An expert panel consisting of a minimum of four assessors – including consultant anaesthetists, DREAMY

study representatives and project board members for NAP5 – will independently evaluate all the responses from patients with possible intraoperative awareness. AAGA events will be graded by consensus opinion in accordance with the Michigan Awareness Classification Instrument [Mashour 2010]. Categorisation for impact on the patient will be in accordance with the NAP5 methodology [NAP5], using the same modified NPSA tool to determine severity of psychological impact. Denominator data, based upon the total number of eligible participants enrolled in the study, will be used to calculate a AAGA event proportion for all recruited patients. Site recruitment logs, detailing numbers of excluded patients or patients that declined to participate, will also be used to provide estimates of how representative this is for all obstetric patients undergoing general anaesthesia. Subgroup analysis for emergency LSCS and other surgical procedures will be performed to determine respective event proportions. Agreement between “Brice positive” classification (based upon Brice questionnaire responses alone) and AAGA classification following full review of the Suspected AAGA follow up responses will be declared.

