9.2 Modified Brice Questionnaire

Screening for AAGA is being assessed in this study using the Brice Questionnaire, which has been adapted from the original published form [Brice 1970] in accordance with common usage [Avidan 2011]. Questions used in the modified Brice questionnaire are available in [Appendix 2](#). Initial screening will be done by local investigator teams, who will be invited to contact the CI or DREAMY Research Team members with any queries regarding Brice response classification. All Local Investigators will be provided with training to ensure that responses are assessed in a consistent manner. In assessing whether a response should be assigned as “Brice positive”, investigators will be instructed to focus on memories of events that could occur only in the operating room during the anaesthetic and surgical periods. Participant reports of memories during the period between "going to sleep" and "waking up" will be taken as “Yes” answers to any of Q3, Q4 or Q5 or “Awareness” to Q6. Any such responses, indicating possible AAGA, require the Local Investigator to follow the Suspected AAGA follow up protocol (see [section 9.3](#)). If an investigator is in any doubt about whether the Brice Questionnaire responses constitute a possible AAGA event, then the responses should be discussed with the local PI and/or CI.

Final classification of Brice responses will be performed by the same expert panel responsible for making final AAGA classification decisions.

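### The Brice-versus-AAGA comparison in section 6.3 is open to inflation because one unmasked panel makes both final calls, and it can yield only a proportion confirmed, not agreement

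*Protocol*

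**What the plan says.** Section 6.3 sets up a comparison of two ratings. The first is Brice-positive status "based upon Brice questionnaire responses alone". The second is described as "AAGA classification following full review of the Suspected AAGA follow up responses will be declared". No statistic is named.

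The ratings are made as follows.

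- **Local Brice call.** Section 9.2: "Initial screening will be done by local investigator teams". The rule counts a Yes to Q3, Q4 or Q5, or choosing Awareness at Q6. Investigators are also told to concentrate on memories that could arise only in theatre.
- **Final Brice call.** Section 9.2: "Final classification of Brice responses will be performed by the same expert panel responsible for making final AAGA classification decisions".
- **AAGA call.** Section 6.3: a panel of at least four assessors "will independently evaluate all the responses from patients with possible intraoperative awareness" and then grades events by consensus.

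Sections 6.2 and 9.3 offer the structured follow-up (Appendix 4) only to women whose Brice answers suggest recall. The comparator group of at least 300 Brice-negative women (sections 6.2 and 6.5) gets the PCL-5 and the risk-factor questions, not Appendix 4.

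**The concern.** There are two separate weaknesses.

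First, the two ratings are not protected from each other. The panel that settles the Brice label also reads the follow-up, and nothing says that the Brice label is settled first or without sight of the interview. A panel that knows a woman's account came to nothing may find it natural to call her Brice form negative as well. Section 6.3 does not say whether the local or the panel label enters the comparison, but section 9.2 calls the panel's label final. If that label is used, unconfirmed local positives can leave the denominator and the screen looks better than it was.

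Second, the second rating exists only for women who screened positive. The Brice-negative row of the two-by-two table is never observed.

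Section 4 justifies Brice as a common comparison tool and a screening method, while noting that its standing as a gold standard is disputed. The section 6.3 comparison is the protocol's only stated check of Brice against full review, so a flattering figure there would be misread as evidence about the screen.

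**Working it through.** The protocol gives no agreement figure, so there is none to reproduce. The check asks which quantities the design determines.

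**Inputs.** Planned sample 2,250 (section 12.2.1). Expected Brice positives about 4, 15 or 118 under the three hypotheses (section 12.2.2). The confirmed share is not given. I assume about 40%, because section 4 reports an earlier obstetric study with 2 definite cases among 5 Brice positives. That source is very imprecise: 2/5 has an exact 95% CI of 5% to 85%. For the smallest scenario I use 2 of 4.

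**Cells.** a = Brice positive and AAGA; b = Brice positive, not AAGA; c = Brice negative and AAGA; d = Brice negative, not AAGA; N = a+b+c+d = 2,250. The follow-up reveals a and b. It does not reveal how a+b falls short of N between c and d.

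**Formulas.** Proportion confirmed = a/(a+b), with Clopper-Pearson interval. Sensitivity = a/(a+c). Kappa = (po − pe)/(1 − pe), where po = (a+d)/N and pe = [(a+b)(a+c) + (c+d)(b+d)]/N².

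**Worked case, a=6, b=9, c=0, d=2,235.** po = 2,241/2,250 = 0.9960. pe = (15×6 + 2,235×2,244)/2,250² = 0.9907. Kappa = 0.57.

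**Varying the unobserved c with a=6, b=9:**

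| c | Proportion confirmed | Sensitivity | Kappa |
|---|---|---|---|
| 0 | 40% | 100% | 0.57 |
| 1 | 40% | 86% | 0.54 |
| 3 | 40% | 67% | 0.50 |
| 5 | 40% | 55% | 0.46 |
| 10 | 40% | 38% | 0.38 |

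**The other two scenarios, c from 0 to 10:**

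| Positives | Confirmed | Proportion (exact 95% CI) | Sensitivity | Kappa |
|---|---|---|---|---|
| 4 | 2 | 50% (7% to 93%) | 100% to 17% | 0.67 to 0.25 |
| 15 | 6 | 40% (16% to 68%) | 100% to 38% | 0.57 to 0.38 |
| 118 | 47 | 40% (31% to 49%) | 100% to 82% | 0.56 to 0.52 |

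The proportion confirmed does not depend on c; kappa and sensitivity do. Setting c = 0 assumes that every unreviewed negative is non-AAGA, which makes sensitivity 100% by construction. Restricting to the 15 positives does not rescue kappa: po = 6/15 = 0.40, pe = (15×6)/15² = 0.40, so kappa = 0, because one rating does not vary.

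**Effect of relabelling (illustration only).** If the panel, having read the interviews, removes k of the 9 unconfirmed women from the Brice-positive group, the reported share becomes 6/(15−k): 40% for k=0, 50% for k=3, 67% for k=6, 100% for k=9. Some removals could be proper on the Brice form alone. A Yes to Q4, for example, may be only a dream, which the section 9.2 rule counts but its theatre-memory instruction would not. Without a locked ruling, a proper removal cannot be told from one prompted by the interview.

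**The case against.** A reader might infer that the comparison cannot be estimated at all. The documents do not support that. The proportion of Brice positives confirmed is estimable, and since section 6.3 names no statistic, agreement could mean just that. A Brice rating free of the panel also exists: local teams apply the Q3 to Q6 rule first, section 9.3 has suspected cases' forms uploaded to REDCap promptly, and the rule can be reapplied to the stored answers. Overturned local positives could therefore be counted, although the protocol does not say that they will be.

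A reader might also infer that the panel will settle the Brice label with the interview in hand. The protocol does not say so. Section 6.3 restricts that label to the Brice answers, and its assessors work independently before consensus. But independence there is between assessors, not between the two ratings, and the stated restriction has no procedure behind it. The risk is real; its size is unknown.

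On the negatives, the objection has force. This is a screen-then-confirm design, AAGA is defined through explicit recall, women are asked up to three times, and the opening question of Appendix 4 presupposes a memory already mentioned. Sensitivity is not a stated aim. The missing row is thus no failure of the study's purpose; it limits what the word agreement can cover.

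The choice of statistic may be left to an analysis plan. The order in which the panel receives papers may not: it is a conduct step that cannot be restored once the interviews have been read.

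**Conclusion.** The concern holds in a limited form. One panel makes both final calls with no stated order or masking, so a comparison that uses its Brice label may be biased upwards by an amount that the documents do not allow anyone to estimate. Separately, the design supports a proportion confirmed but not overall chance-corrected agreement or sensitivity, unless all unreviewed negatives are taken as non-AAGA. At 15 positives with 6 confirmed, up to 10 missed cases would move kappa by about 0.19 (0.57 to 0.38) while the proportion confirmed stayed at 40%. At 118 positives the movement is small (0.56 to 0.52). These sizes rest on the assumed confirmation rate and the assumed values of c.

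The comparison is descriptive and appears in neither section 12.1.1 nor 12.1.2, so importance is modest. The change is worth making because it is cheap and only works if made before panel review.

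**What to change.** In sections 6.3 and 9.2:

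1. State that the panel classifies each Brice form on its own and records a locked ruling before the Appendix 4 responses for that woman are released to it.
2. Report the proportion confirmed as AAGA, with an exact confidence interval, in two groups: local Brice positives under the Q3 to Q6 rule as recorded at screening, and panel-locked Brice positives. The first shows how the screen performed in use; the second shows what expert reading of the same form adds.
3. Report how many local positives the panel's locked ruling overturned.
4. Call the result the proportion confirmed, or positive predictive value, rather than agreement. Say that Brice-negative women were not reviewed, so sensitivity and overall agreement are not estimated.

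The cost is a two-step release of papers to the existing panel and a few reworded sentences, with no extra assessors or patient contact. The panel process becomes slightly longer, and the figure may be less favourable. The change gives no information on the negatives; it only stops the report from implying any.

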9.3 Suspected AAGA follow up protocol

Any patient with Brice questionnaire responses indicating possible memories during the anaesthetic episode will be provided with a secondary structured interview schedule/questionnaire to further detail the characteristics and psychological response to their experience (based upon questions in [Appendix 4](#)).

All suspected AAGA cases should be discussed with the local PI or CI. The local investigator or PI should upload the modified Brice CRF responses to the DREAMY REDCap Server as a matter of urgency (ideally on the same day as reported). An explanation of the subsequent DREAMY follow up procedures should be offered to the participant, alongside a choice of initial telephone/face-to-face structured interview schedule or paper questionnaire. The Local Investigator should notify the CI and/or DREAMY Research Team that they have identified a participant with suspected AAGA.

If the participant chooses a paper questionnaire, then this will be administered by the Local Investigator team whilst the participant is still in hospital. Responses are to be transferred according to arrangements with the DREAMY Research Team (to be couriered, collected by a member of the team or transmitted using secure NHS.net email).

If the participant chooses a structured interview schedule, then this can be conducted via telephone or face-to-face. Suspected AAGA interviews will be led by the CI or DREAMY Research Team at the earliest available opportunity. Any travel expenses incurred will be reimbursed to participants.

All Suspected AAGA structured interview schedules and questionnaires are adapted from those used in BAG-RECALL trial [Avidan 2011]) and feature categorical and free-text responses on the detail and nature of recalled events and experiences during anaesthesia, alongside self-reported perioperative context and post-operative psychological consequences.

All suspected AAGA patients will also be offered the PCL-5 PTSD checklist ([Appendix 5](#)) at day 30, 3, 6, 9 and 12 months following the index anaesthetic episode. The checklist will be administered via telephone by the DREAMY Research Team (although written forms or face-to-face will be provided if requested). During first administration of the PCL-5 checklist additional target information will be obtained using a structured and multi-dimensional questionnaire on the woman's self-reported mental health history, infant's health status and psychological experiences in the gravidic-puerperal cycle. Question domains have been derived from known risk factors for developing PTSD during the post-natal period [Andersen 2012] and will also be asked to the comparator sample of 300 non-AAGA patients collected during the early phase of the study (see [Section 6.5](#)).

An extended AAGA follow up will occur during the 3 month PTSD follow up episode, with a view to investigating the nature of local clinical follow up received by patients and how the AAGA episode has impacted on attitudes towards future anaesthetics and post-natal experience (see [Appendix 7](#) for questions used).

[figure not shown]

Figure 4. Suspected AAGA Follow Up flowchart

10 Data management and quality assurance

10.1 Confidentiality

All data will be handled in accordance with the Data Protection Act 1998.

In order to facilitate follow up of patients at 30 days (i.e. post-hospital discharge) participant's name, contact details and relevant previous study questionnaire responses will be shared between the site of recruitment and by the DREAMY Research Team (Clinical Trial Assistants

(CTA)/Research Nurses at the St. George's Hospital Clinical Research Facility). Data will not be shared between recruitment sites. Confidential patient identifiers will be held for the minimal necessary period. Once 30 day Brice follow up is complete and no suspicion of AAGA is confirmed, patient identifiers may then be deleted from the database record. After data capture for the study has completed, all personal identifiable data will be deleted and the anonymised data transferred to a data safe haven approved by the Sponsor for final analysis and data storage. The electronic study data will be deleted confidentially after a specified time point (10 years after the end of the study).

10.2 Data collection tool

Case Report Forms have been designed by the CI and approved by the protocol authors. All data will be entered legibly in black ink with a ball-point pen. If the Investigator makes an error, it will be crossed through with a single line in such a way to ensure that the original entry can still be read. The correct entry will then be clearly inserted. The amendment will be initialled and dated by the person making the correction immediately. Overwriting or use of correction fluid will not be permitted.

It is the Investigator's responsibility to ensure the accuracy of all data entered and recorded in the CRFs. The Staff Delegation of Responsibilities Log JREOLOG0004 will identify all study personnel responsible for data collection, entry, handling and managing the database.

Data collection tools are used along the following schedule:

| Timing | Data collection | Format | Responsible |
|---|---|---|--|
| 0-24h | Modified Brice Questionnaire (repetition 1) | Written questionnaire | Local investigators |
| 24-48h | Modified Brice Questionnaire (repetition 2) | Written questionnaire | Local investigators |
| Any time (ideally 0-48h) | Anaesthetic Episode data collection | Written CRF | Local investigators |
| Any time "Brice +ve" responses identified | Suspected AAGA Questionnaire | Telephone structured interview schedule (or face-to-face structured interview schedule or written questionnaire) | DREAMY Research Team (if identified at Day 30) or Local Investigators (if inpatient) |
| Day 30 (+/- 5 days) | Modified Brice Questionnaire (repetition 3) | Telephone structured interview schedule (or written questionnaire) | DREAMY Research Team |

| | | | |
|---------------------|---|---|----------------------|
| Day 30 (+/- 5 days) | If "Brice positive": PCL-5 Post-Traumatic Stress Checklist Post-natal PTSD risk factors questions | Telephone structured interview schedule (or written questionnaire) | DREAMY Research Team |
| 3 months | If "Brice positive": PCL-5 Post-Traumatic Stress Checklist AAGA Extended follow up | Telephone structured interview schedule (or written questionnaire) | DREAMY Research Team |
| 6 months | If "Brice positive": PCL-5 Post-Traumatic Stress Checklist | Telephone structured interview schedule (or written questionnaire) | DREAMY Research Team |
| 9 months | If "Brice positive": PCL-5 Post-Traumatic Stress Checklist | Telephone structured interview schedule (or written questionnaire) | DREAMY Research Team |
| 12 months | If "Brice positive": PCL-5 Post-Traumatic Stress Checklist | Telephone structured interview schedule (or written questionnaire) | DREAMY Research Team |

10.3 Incidental findings

Any findings of relevance to ongoing clinical care will be shared with local care teams, provided participant consent is provided. Local clinical representatives in anaesthesia, obstetrics and midwifery will facilitate the further management and clinical care of participants in the study.

10.4 Data handling and analysis

All data collected, analysed and stored for DREAMY will remain strictly confidential. Data handling will comply with Good Clinical Practice guidelines, the Data Protection Act 1998 and the NHS code of confidentiality.

All data will be collected on paper data case report forms (CRFs). Identifiable patient data will be collected to facilitate follow up at 30 days and referral of any patients with AAGA or other incidental findings back to the local clinical care team.

CRF responses will be taken directly to a secure location accessible by the local Principal Investigator (or Local Investigator) who will enter the data from the paper data collection form onto a secure web-based portal for the study database. All information in paper format for the study will be held securely and treated as strictly confidential in accordance with NHS policies. Data will be entered electronically via a secure encrypted connection into an online portal hosted by St. George's University of London. The software used for data capture will be REDCap™ (Research Electronic Data Capture – <http://www.project-redcap.org>) [Harris 2009]. REDCap is a mature, secure web application for building and managing online surveys and databases. Access to the

REDCap data entry system will be protected by username/password and created during the Local Investigator registration process.

Confidential patient identifiers will be held for the minimal necessary period. Once 30 day Brice follow up is complete and no suspicion of AAGA is confirmed patient identifiers may then be deleted from the database record.

Adherence to the Sponsor SOP on Data Management JREOSOP0038 will be maintained.

11 Archiving arrangements

The study essential documents along with the study database will be archived in accordance with the sponsor SOP JREOSOP0016. The agreed archiving period for this study will be 10 years. This will include any study databases.

Each PI at any participating site will archive the study essential documents generated at the site for the agreed archiving period

12 Statistical design

12.1 Endpoints

12.1.1 Primary endpoints

The primary endpoint is the proportion of obstetric GA patients reporting AAGA in the included sample.

12.1.2 Secondary endpoints

The secondary endpoints are:

1. Descriptors of anaesthetic, surgical and patient factors associated with AAGA
2. 3, 6, 9 and 12 month results of the Post-Traumatic Stress Disorder Checklist (PCL-5), for patients with confirmed AAGA. This will be compared with PTSD incidence in the initial cohort of non-AAGA participants.
3. Qualitative description of the experience of AAGA undergone by obstetric patients.

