2. 0-24h following index GA = Written consent obtained. Modified Brice questionnaire (repetition 1). Data collected for the anaesthetic episode.
3. 24-48h following index GA = Modified Brice questionnaire (repetition 2).
4. Day 30 (+/- 5 days) from index GA = Modified Brice questionnaire (repetition 3).

If a participant reports possible recall of events during the anaesthetic episode (“Brice positive”):

1. Participants will be offered a further Suspected AAGA structured interview schedule or questionnaire (adapted from the BAG-RECALL trial [Avidan 2011]). Questionnaires are available in paper form for distribution to inpatients by Local Investigators. Interviews can be conducted via telephone or face-to-face. Suspected AAGA follow up will be made at the earliest available opportunity and in a format of the participant’s preference.
2. “Brice positive” notification will be shared between the local clinical teams and the DREAMY Research Team.
3. Local clinical care teams will be encouraged to offer care in accordance with the NAP5 awareness support pathway [NAP5 Anaesthesia Awareness Support Pathway].
4. Post-Traumatic Stress Disorder (PTSD) Checklist (PCL-5) at day 30, 3, 6, 9 and 12 months.
5. Post-natal PTSD risk factor questions at day 30.
6. AAGA Extended follow up at 3 months, exploring patient attitudes and post-AAGA clinical support.

An initial minimum sample of the first 300 Brice -ve patients completing day 30 follow up will also receive:

1. PCL-5 checklist and targeted questions on risk factors for post-natal PTSD at day 30. This provides a comparator group for PTSD incidence and baseline characteristics in the post-natal period for AAGA vs. non-AAGA patients.

Figure 2. Summary of in-hospital, telephone and conditional DREAMY data collection procedures

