6.5 Comparator sample for PTSD follow up at 30 days

To provide a baseline incidence of PTSD symptoms in patients undergoing obstetric surgery under GA but who do not experience AAGA, an initial sample of participants will also be asked to complete the PCL-5 checklist and post-natal risk factors for PTSD questionnaire at 30 days. Data collection for this comparator sample will end once at least 300 participants have provided responses.

[figure not shown]

Figure 3. Flowchart of methodology for local investigators

7 Participant Selection criteria

There will be no exceptions (waivers) to eligibility criteria prior to participant inclusion into the study. Any questions raised about eligibility should be addressed prior to entering the participant.

The eligibility criteria have been carefully considered and are standards used to ensure the study results can be appropriately used to make future treatment decisions for other people with similar disease or medical condition. It is therefore vital that exceptions are not made to the following detailed selection criteria.

All participants that are screened for inclusion into the study must be entered onto the Sponsor screening log JREOLOG0001 and will be assigned a sequential number. Participants will be considered eligible for enrolment into this study if they fulfil all the inclusion criteria and none of the exclusion criteria as defined below.

Eligible participants will be entered onto the Sponsor's Subject ID log JREOLOG0002 and assigned a trial specific Identification number in a pre-agreed format in accordance with site identifier and next sequential numerical value e.g. SG001.

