No formal estimate is made for the sample size of the baseline comparator group of non-AAGA patients who will be undergoing PTSD screening at 30 days. A lack of clear evidence regarding PTSD prevalence in patients receiving general anaesthesia for obstetric surgery would make such estimations speculative. Therefore, sample size has been preferentially determined by operational issues and consideration of sample size of studies identified in a previous systematic review of post-natal PTSD [Anderson 2012].

12.2.2 *Primary endpoint analysis*

The proportion of obstetric GA patients reporting AAGA will be expressed using binomial confidence intervals and compared with established values (see above for rectification of sample size).

There are three competing hypotheses. First, that the event proportion of Brice positivity in obstetrics is similar to that of the general population (i.e. ~1:660). If so, then we expect ~4 patients (binomial 95% CI 1 – 10). Second, that our incidence of Brice positivity will be similar to Paech’s already reported incidence (i.e. ~1:152 [Paech 2008]). Then we expect ~15 (95% CI 8 – 25) patients. Third, that the ratio between “Brice positive” and spontaneous reporting as in the general population (i.e. 1:660 vs 1:19,000) is maintained for obstetric patients (i.e. ~1:19). Then we expect 118 patients (95% CI 98 – 141). These figures for each of the three possible outcomes will be compared using Fisher’s exact test or chi-squared testing to yield a definitive answer as to which is the most likely hypothesis of the three.

Because we are administering the Brice questionnaire during 0-24h following the index GA (i.e. as soon as possible after GA recovery), we expect to obscure those cases who may otherwise report spontaneously. In other words, we do not expect by our methods to detect spontaneous reporting as such, as the questions will already have been asked. It is possible that some few patients may telephone in after their discharge to report that they now recall AAGA, perhaps triggered by the study, but even that would not fulfil the criterion for spontaneous reporting. We plan to class any such cases as “triggered reporting” and analyse them separately.

Subgroup analysis of the AAGA proportion will be conducted for type and urgency of surgical procedure (including emergency LSCS), de novo conversion from regional anaesthesia to GA and for GA inductions using propofol vs. thiopental.

12.2.3 *Secondary endpoint analysis*

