For secondary outcomes of interest, data will be presented as a number or percentage; mean and standard deviation (SD) for normally distributed data and median and interquartile range (IQR) for non-parametric data, with 95% confidence intervals (CI). Significance of associations with anaesthetic, surgical and patient factors will be tested using relevant measures of correlation. If sufficient AAGA events are identified, then a multivariable regression model will be used to evaluate the independent association of specific anaesthetic episode variables with AAGA, with results expressed as odds ratios (ORs).

Post-Traumatic Stress Disorder Checklist (PCL-5) results will be expressed as a total symptom severity score (range = 0-80), obtained by summing the scores from each of the 20 checklist items. PCL-5 questions are grouped into 4 domains referring to different symptom criteria: 5 questions refer to symptoms of re-living (cluster B), 2 to avoidance behaviour (cluster C), 7 to emotional blunting (cluster D) and 6 to symptoms of hyper-excitability (cluster E). Symptoms are considered significant when the person scores 2 or more on the item. Women will be considered positive on the PCL-5 when they have at least 1 significant symptom for cluster B, at least 1 for cluster C, at least 2 cluster D items and 2 cluster E [Blevins 2015, National Centre for Posttraumatic Stress Disorder]. PTSD prevalence rates will be estimated for the entire sample and certain subgroups, including AAGA and non-AAGA patients. Results will be expressed with the respective 95% confidence intervals. Fischer's exact test will be used to test the homogeneity of prevalence rates in the subgroups.

Case descriptions of the experiences of AAGA undergone by patients with AAGA will be presented in anonymised format. The phase of anaesthesia/surgery when the AAGA event occurred, alongside possibility contributory, causal or mitigated factors, will be described where possible.

13 Direct access to source data

The Investigator(s)/institution(s) will permit study-related monitoring, audits, REC review, and regulatory inspection(s), providing direct access to source data/documents. Study participants are informed of this during the informed consent discussion. Participants will consent to provide access to their medical notes.

14 Ethics and regulatory requirements

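### Secondary endpoint 2 sets AAGA patients' PCL-5 at 3 to 12 months against a non-AAGA cohort measured only at day 30, so that comparison mixes AAGA with time since birth

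*Protocol*

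**What the plan says.** Section 12.1.2 defines the second secondary endpoint as "3, 6, 9 and 12 month results of the Post-Traumatic Stress Disorder Checklist (PCL-5), for patients with confirmed AAGA" and continues: "This will be compared with PTSD incidence in the initial cohort of non-AAGA participants".

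The comparator is described in three places, each time with a single assessment:

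- Section 6.2 (Figure 2 summary): the first 300 or more Brice-negative women who reach day-30 follow-up receive the "PCL-5 checklist and targeted questions on risk factors for post-natal PTSD at day 30".
- Section 6.5, whose title itself refers to 30 days: "Data collection for this comparator sample will end once at least 300 participants have provided responses".
- Section 12.2.1: a "baseline comparator group of non-AAGA patients who will be undergoing PTSD screening at 30 days".

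Brice-positive women follow a longer schedule. Section 6.2 lists for them "Post-Traumatic Stress Disorder (PTSD) Checklist (PCL-5) at day 30, 3, 6, 9 and 12 months". The table in 10.2 restricts the visits at 3, 6, 9 and 12 months to Brice-positive women. For women without suspected AAGA, 10.4 says that once day-30 follow-up is complete and "no suspicion of AAGA is confirmed patient identifiers may then be deleted from the database record".

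On analysis, 12.2.3 plans PTSD prevalence by subgroup, including AAGA and non-AAGA, and says that Fisher's "exact test will be used to test the homogeneity of prevalence rates in the subgroups". It names no time point for that test.

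**The concern.** The two sides of the comparison in 12.1.2 share no time point. If PTSD symptoms change between one month and one year after birth, for whatever reason, that change enters the contrast as though AAGA had caused it. A natural decline would hide harm or even make AAGA look protective. A natural rise would exaggerate harm.

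The psychological consequences of AAGA are the stated secondary aim (5.2), and this is the only comparison between AAGA and non-AAGA women written into the PCL-5 endpoint. A reader of the final report would take a 12-month figure set against the cohort as evidence about AAGA, which it could not be.

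**Working it through.** **1. The schedules side by side** (6.2, 6.5, 10.2, 12.1.2, 12.2.1)

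| PCL-5 | Day 30 | 3 mo | 6 mo | 9 mo | 12 mo |
|---|---|---|---|---|---|
| Collected, Brice-positive | yes | yes | yes | yes | yes |
| Collected, comparator | yes | no | no | no | no |
| Named in 12.1.2 for AAGA patients | **no** | yes | yes | yes | yes |

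The endpoint uses four time points that the comparator lacks and omits the one that both groups have.

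**2. What the stated contrast estimates**

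The protocol gives no effect size or power for this comparison, so there is no planned figure to reproduce. On the odds scale:

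odds(AAGA, late) / odds(non-AAGA, day 30) = [odds(AAGA, late) / odds(non-AAGA, late)] × [odds(non-AAGA, late) / odds(non-AAGA, day 30)]

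The first factor is the AAGA effect and the second is the time trend. Neither can be estimated separately, because non-AAGA women are never measured late. Borrowing the trend from the AAGA women's own day-30 values does not help: dividing by odds(AAGA, late) / odds(AAGA, day 30) leaves odds(AAGA, day 30) / odds(non-AAGA, day 30), which is the day-30 contrast.

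**3. Illustration with no AAGA effect**

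Assumed, not in the documents: prevalence of a positive PCL-5 is 10% at day 30 and 10%, 5% or 3% at the late visit, the same in both groups.

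- Fall to 5%: (0.05/0.95) / (0.10/0.90) = 0.0526 / 0.1111 = **0.47**
- Fall to 3%: (0.03/0.97) / (0.10/0.90) = 0.0309 / 0.1111 = **0.28**
- In the other direction, a rise from 5% to 10%: 0.1111 / 0.0526 = **2.11**

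The table gives the probability that a two-sided Fisher's exact test at 0.05 rejects, by exact enumeration. It takes 300 comparators at 10% (size from 6.5) and the AAGA numbers expected under the three hypotheses in 12.2.2.

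| AAGA women | No trend (10%) | Late 5% | Late 3% |
|---|---|---|---|
| 4 | 2.3% | 0.6% | 0.2% |
| 15 | 2.6% | 0.2% | 0.03% |
| 118 | 4% | 34% | 70% |

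With 118 women the false finding is often significant. With 4 or 15 it almost never is, but the odds ratio is biased by the same factor.

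**4. Illustration with a true odds ratio of 3** (also assumed)

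- Late background 5%: apparent odds ratio 3 × 0.474 = 1.42
- Late background 3%: apparent odds ratio 3 × 0.278 = 0.84

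With 118 AAGA women, power against the day-30 cohort is 17% or 6%. Against 300 comparators measured at the same late visit it would be 79% or 60.5%.

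The counts in 12.2.2 are expected Brice-positive women. The endpoint concerns confirmed AAGA, and no loss to follow-up is allowed for, so actual numbers may be smaller.

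**The case against.** The strongest reply is that the study does contain a like-for-like comparison. Brice-positive women complete the PCL-5 at day 30, and the Figure 2 summary in 6.2 presents the day-30 sample as the reference group for comparing women with and without AAGA. Section 12.2.3 names no time point for Fisher's test, so a day-30 test fits within the plan. This stands, and it limits the point. A reader might infer that the study cannot separate AAGA from time at all. The documents do not support that: the fault lies in the comparison stated in 12.1.2, not in the data collection.

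It does not rescue 12.1.2 itself, which names its time points and its comparator explicitly. It is not a detail left for a later analysis plan, and 12.2.3 does not correct it.

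A reader might also infer that an unadjusted test of a yes/no screen is the wrong analysis. That is not established. Section 12.2.3 also reports the 0 to 80 score, covariate adjustment is commonly left to an analysis plan that is not shown here, and Fisher's test is valid with sparse cells. With perhaps 4 to 15 exposed women, an adjusted model would be a debatable preference.

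Finally, the direction and size of any time trend are unknown. The figures above show what could happen, not what will.

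**Conclusion.** The point holds for the comparison as written in 12.1.2: AAGA status and time since birth are completely confounded there, at any sample size. That conclusion follows from the schedules alone. The magnitude rests on assumed prevalences. Under a fall from 10% to 5% or 3%, the spurious odds ratio is 0.47 or 0.28, with false rejection in 34% or 70% of studies at 118 AAGA women and in under 1% at 15. A rise would push the estimate the other way, and with no trend the problem disappears.

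This should be fixed, but it is not critical. It concerns a secondary endpoint in a descriptive study, the primary endpoint is untouched, the matched day-30 data are already planned in both groups, and the repair is a change of wording.

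**What to change.** In 12.1.2 and 12.2.3, state that AAGA and non-AAGA women are compared on day-30 PCL-5 in both groups. The planned Fisher's test can stay, with day 30 named as its time point. Report the 3, 6, 9 and 12 month PCL-5 results descriptively within AAGA patients, and remove their comparison with the day-30 cohort.

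No new data, visits or participants are needed. The cost is that the study makes no between-group claim beyond day 30. If the sponsor wants such a claim, the comparator would need later PCL-5 assessments, arranged before its identifiers are deleted under 10.4. That would be an extension of the study rather than a correction of wording.
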